10.5.2.2 Urinalysis

Individual urinalysis data will be listed.

Blood, protein and glucose will be graded in the following manner: 0='0 or Trace', 1='1+', 2='2+', 3='3+', 4='4+'. The number and percent of subjects by worst post-dose levels will be presented for blood, protein and glucose in the urine).

10.5.3 Vital Signs

Vital signs data will be reviewed for each subject. Depending on the size and scope of the changes, the analyses of vital signs may include summary statistics over time and/or changes from baseline over time by dose cohort.

10.5.4 Eastern Cooperative Oncology Group (ECOG) Performance Status

ECOG performance status scores will be summarized at each assessed time point. The change in scores from screening to safety follow-up (end of study) or last post-baseline value (if safety follow-up is not available) will also be summarized.

10.5.5 Antibody Formation

The presence of anti-blinatumomab binding antibodies will be assessed using a validated assay. The incidence of anti-blinatumomab antibodies will be listed for each subject. The number and percentage of subjects who have developed

anti-blinatumomab antibodies (binding and if positive, neutralizing) at any time, at baseline and during post-baseline visits will be summarized by dose cohort.

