- k **Creatinine clearance to be calculated by Cockcroft-Gault equation.**
- l Lymphocyte subsets for the study are listed above in SOA and are to be collected prior to administration of IP on days 1 and 22, however, additional samples will be collected for adverse events of CTCAE  $\geq$  grade 3 neuro toxicity and CRS occurs throughout the study at the start and resolution of the event (**refer to Section 7.3.16.1**).
- m Disease assessments are to be performed to establish staging and response per Cheson **if disease assessment is by CT scans (Appendix A)** and Lugano criteria **if disease assessment includes PET/CT (Appendix B)**. For PET-CT, CT, or contrast enhanced CT the same imaging modality should be used throughout the study for an individual subject. Disease assessment to occur: during screening; just prior to optional cycle 2 if given (attempt to obtain this study at least 2 weeks after stopping IP in cycle 1 and just prior to starting cycle 2); and the last disease assessment is 4 weeks after finishing the last dose of IP. If PET and CT are acquired on the same day, it is strongly recommended that PET is performed prior to the CT with IV contrast.
- n Bone marrow biopsy to be performed according to Cheson ([Appendix A](#)) and Lugano criteria ([Appendix B](#) [standard of care per investigator]).
- o Bone marrow biopsy performed within 21 days of the first dose of IP may be used in place of screening assessment to establish staging or response per Cheson ([Appendix A](#)) and Lugano criteria ([Appendix B](#)).
- p Anti-blinatumomab antibody predose on day 1, before the administration of first SC dose (following 12 hour wash out from cIV), and predose at the re-start of cIV infusion (following the 2 to 3 day washout).
- q **Cytokine sample on days 1 and 22: predose and at the following time points postdose, 2 hours ( $\pm$  15 minutes), 4 hours, 6 hours ( $\pm$  30 minutes for both the 4 and 6 hour time points), and 12 hours (before the next injection in case of q12h dosing  $\pm$  1 hour). Additional samples will be collected for adverse events of CTCAE  $\geq$  grade 3 neuro toxicity and CRS occurs throughout the study at the start and resolution of the event (Refer to [Section 7.3.16.2](#)).**

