2.2 Secondary Objectives

- To determine pharmacokinetics (PK) with continuous intravenous (cIV) and SC administrations
- To estimate the maximum tolerated dose (MTD) tested for blinatumomab administered subcutaneously
- To determine the incidence of anti-blinatumomab antibody formation following SC administration
- To evaluate efficacy response following treatment with SC blinatumomab administration

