3.1 Study Design

This is a global multi-center, Phase 1b open-label study investigating the safety and PK of blinatumomab administered subcutaneously for the treatment of relapsed/refractory indolent NHL. The SC administration of blinatumomab will be tested for the first time in humans.

Period 1 of the study will focus on the determination of PK, bioavailability, and safety profile of blinatumomab SC administration. The PK and bioavailability data from Period 1 of the study will be used in conjunction with safety data (DLT) to determine the SC

MTD. The MTD or the maximum tested dose, if MTD is not reached, will be further tested in Period 2 in an expanded cohort. Efficacy of blinatumomab administered subcutaneously will also be investigated in each period of the study.

3.1.1 Cycle 1/Period 1

In Period 1, 3 or more separate dose cohorts of up to 6 DLT evaluable subjects each will be enrolled and undergo treatment as follows:

- Subjects will undergo an initial cIV blinatumomab run-in period (weeks 1 to 3) followed by a 12-hour treatment free period.
- Subjects will then receive SC administration (week 4) followed by a treatment free period of 2 to not more than 3 days.
- After the SC administration period, subjects should return to receive cIV treatment to complete 6 weeks of therapy (weeks 5 to 6).

For all cohorts, the initial cIV dose of blinatumomab will be 9 µg/day for the first 7 days (to mitigate for potential cytokine release syndrome [CRS] and neurologic events associated with introduction to blinatumomab) which then will be escalated (dose-step) to 28 µg/day starting on day 8 through day 14 (week 2), and to 112 µg/day starting on day 15 until day 21 (week 3).

After stopping cIV blinatumomab, there is a 12-hour treatment free period before starting SC blinatumomab. SC blinatumomab starts after the 12-hour treatment free period and will be administered (week 4) as the following dose-cohort levels:

- Dose Cohort 1: 112 µg q12h × 5 days for a total of 9 doses (n= 6)
- Dose Cohort 2: 225 µg q12h × 5 days for a total of 9 doses (n = 6)

(Note: A total of 9 SC doses will be given for the q12h dosing, so intensive PK samples can be obtained on day shift to reduce errors).

- Dose Cohort 3: 450 µg q24h × 5 days for a total of 5 doses (n = 6)
- Additional Dose Cohorts: Dose level and dosing frequency to be determined as described below

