One or more dosing regimens (refer to Dosing Schema Figure 1 in protocol) may be selected based on clinical findings including safety, tolerability, and PK results from previous cohorts; and after Dose Level Review Team (DLRT) review and make recommendations for the next SC cohort dose and frequency. The dose may be increased (by 1 dose level or between the dose of the previous cohort and the next higher dosing level in Figure 1 schema in protocol), kept at the same dose level or decreased by 1 or more dose levels. The dose frequency chosen (q12h, q24h, q48h,

q72h, q96h, or q7days) will be decided by the DLRT and will be based on the previous cohort PK data.

Once the SC dosing is complete, a treatment free period of 2 to not more than 3 days between stopping SC and restarting cIV will be observed. Then the cIV blinatumomab dosing will resume at 112 µg/day (weeks 5 to 6) to complete 6 weeks of treatment.

For each SC dose cohort, if ≤ 1 of the 6 DLT evaluable subjects experience a DLT during the SC administration DLT evaluation period then the dose will be determined to be tolerable and the DLRT will decide the next dose level to be initiated and the frequency of administration for the next cohort; see Section 6.2.1.2.2 in protocol for definition of the DLT evaluation period.

For each SC dose cohort, if ≥ 2 of the 6 DLT evaluable subjects experience a DLT during the SC administration then dosing will stop for individual subjects who experience a DLT, a DLRT meeting will be conducted, and further steps will be determined, such as dose de-escalation or increasing dosing interval (Figure 1 in protocol). In addition, if subjects on this cohort have not reached the SC dosing, they will be allowed to stay on study but will finish cycle 1/period 1 as cIV.

MTD will be defined as the highest dose level at which ≤ 1 of 6 subjects experience a DLT. If no subject experiences a DLT, the MTD will be defined as the maximal dose tested.

For further details, see Section 6.2.1.2.1 and Section 6.2.1.2.3 of protocol.

3.1.2 Cycle 1/Period 2

The aim of Period 2 will be to assess the MTD as derived from Period 1, or the maximum tested dose, if MTD has not been reached, for additional safety and preliminary efficacy data in an expanded cohort of up to 15 evaluable subjects receiving SC treatment only (no cIV run-in).

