4.2 Planned Covariates

The relationship of the certain baseline covariates to endpoints will be explored if appropriate. Biomarker data may be incorporated in additional exploratory subgroup or multivariate analyses. The analyses of biomarkers may be performed after collection of all samples during the conduct of the study and therefore may be reported after the final analysis.

5. Hypotheses and/or Estimations

No formal statistical hypothesis will be tested.

The clinical hypothesis is that blinatumomab administered through the SC route will demonstrate a tolerable safety-profile with serum concentrations comparable to those for which efficacy was shown with cIV administration in subjects with indolent relapsed/refractory Non-Hodgkin's Lymphoma (NHL).

6. Definitions

Age at Enrollment

Subject age at enrollment will be collected in years in the clinical database.

Baseline

For the analysis of all endpoints, baseline will be defined as the value measured on day 1 of the first cycle of blinatumomab. If a day 1 value is not available, the most recent value before the day of the start of any protocol-specified therapy may be used.

Best Overall Response

Best overall response for a subject is determined as ORR (CR+PR) using Cheson ([Appendix B](#)) and Lugano criteria ([Appendix C](#)) during the Safety Follow-up visit (2 to 4 weeks after the end of therapy for cycle 1). In the case where a second cycle is administered, the assessment has to be done prior to the start of the next cycle to assess the evolution of disease (as close to 2 weeks after the last dose of IP cycle 1, but before starting cycle 2).

Change From Baseline

Change from Baseline is the arithmetic difference between post-Baseline and Baseline values.

Disease Related Events

Disease Related Events are events (serious or non-serious) anticipated to occur in the study population due to the underlying disease eg, disease progression ([Table 3](#)). Such events do not meet the definition of an adverse event unless assessed to be more severe than expected for the subject's condition.

Disease Related Events that do not qualify as Adverse Events or Serious Adverse Events:

- An event which is part of the normal course of disease under study (eg, disease progression in oncology or hospitalization due to disease progression) is to be reported as a Disease Related Event.
- Death due to the disease under study is to be recorded on the event CRF.

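### In Period 1 no planned antibody summary isolates antibodies formed after subcutaneous dosing, which is what the secondary objective asks for

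*SAP*

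**What the plan says.** The objective is route-specific: "To determine the incidence of anti-blinatumomab antibody formation following SC administration" (SAP Section 2.2; Protocol Section 1.2 agrees). The endpoint in SAP Section 4.1.2 is only the incidence of antibodies, with no route named. SAP Section 10.5.5 lists results for each subject. It then counts subjects who have developed binding antibodies (and, if positive, neutralizing antibodies) "at any time, at baseline and during post-baseline visits will be summarized by dose cohort".

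Four other provisions decide what those counts contain.

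- **Baseline** (SAP Section 6): for all endpoints, "baseline will be defined as the value measured on day 1 of the first cycle of blinatumomab".
- **Period 1 sequence** (SAP Section 3.1.1): "Subjects will undergo an initial cIV blinatumomab run-in period (weeks 1 to 3) followed by a 12-hour treatment free period". SC dosing follows in week 4, and cIV then resumes in weeks 5 to 6.
- **Period 1 antibody samples** (Protocol Table 3 and its footnote p): "Anti-blinatumomab antibody predose on day 1, before the administration of first SC dose (following 12 hour wash out from cIV"), then "predose at the re-start of cIV infusion (following the 2 to 3 day washout"), then safety follow-up.
- **Analysis set** (SAP Sections 7 and 7.1): unless stated otherwise, everyone who receives blinatumomab. Section 10.5.5 states nothing different.

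In Period 2, cycle 1 is SC only. Antibodies are sampled before the first dose on day 1, weekly in weeks 3 to 6, and at follow-up (Protocol Table 5 and footnotes). If a second cycle is given, follow-up moves to the end of cycle 2 and there is a predose sample on day 1 of cycle 2 (Protocol Table 7).

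**The concern.** The study is the first to give blinatumomab subcutaneously. Protocol Section 2.5 says that no antibodies have been seen in NHL under cIV and that the incidence with SC will be examined here. A reader will therefore look to this endpoint for what SC dosing adds.

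In Period 1 the planned counts cannot show that directly. A subject who turns positive during the cIV run-in is a post-baseline positive without having had any SC drug. A subject who turns positive after cIV resumes is counted in the same way. A subject who stops during the run-in adds to the denominator without ever being at risk.

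The SAP separates routes elsewhere: for Period 1 adverse events (Section 10.5.1), exposure (10.5.6), PK (10.7) and PD (10.8). It does not do so for antibodies, although the protocol draws samples immediately before and after the SC week.

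**Working it through.** The documents give no rate, precision or sample size for antibody incidence, so there is no planned figure to reproduce. The check sets the sampling schedule against the definitions.

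**Period 1, cycle 1: four scheduled samples**

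| Sample | Exposure so far | Any time | Baseline | Post-baseline |
|---|---|---|---|---|
| Day 1 predose | none | yes | yes | no |
| Day 22 predose | cIV, 3 weeks | yes | no | yes |
| Day 29, before cIV restart | cIV, then SC | yes | no | yes |
| Safety follow-up | cIV, SC, then cIV | yes | no | yes |

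- Any-time count: 2 of 4 samples precede SC.
- Post-baseline count: 1 of 3 precedes SC, 1 of 3 follows SC but precedes further cIV, and 1 of 3 follows further cIV.
- Only the day 29 sample is both after SC and before cIV resumes. It falls 29 − 22 = 7 days after the first SC dose.

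**Period 2, cycle 1**

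The one pre-SC sample is day 1, which is baseline. Of the five later samples (weeks 3, 4, 5, 6 and follow-up), 0 of 5 precede SC.

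**Effect of one pre-SC positive (assumed, for illustration)**

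Take a Period 1 cohort of 6, all given SC, with one subject first positive at day 22 and no new positives after SC. Intervals are exact Clopper-Pearson 95%.

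- Any-time and post-baseline counts: 1/6 = 16.7% (0.4% to 64.1%).
- SC-emergent count: 0/5 = 0%, with upper limit 1 − 0.025^(1/5) = 52.2%.

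**How often this could happen**

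The chance of at least one pre-SC positive among n subjects is 1 − (1 − q)^n. The documents give no value for q, so the values below are assumptions.

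| Assumed q | n = 6 | n = 30 |
|---|---|---|
| 1% | 5.9% | 26.0% |
| 2% | 11.4% | 45.5% |
| 5% | 26.5% | 78.5% |
| 10% | 46.9% | 95.8% |

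Protocol Section 2.5 points to the top row or below.

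**Denominator**

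Protocol Section 3.3 plans about 54 enrolled to yield 30 + 15 = 45 evaluable, a ratio of 54/45 = 1.2. Spread evenly, that is 6 × 1.2 = 7.2 per Period 1 cohort. If one of seven treated subjects stops in the run-in and one of the other six forms antibodies after SC, the full analysis set gives 1/7 = 14.3%, against 1/6 = 16.7% among those given SC. Subjects switched to cIV only after two DLTs in their cohort (Protocol Section 3.1.1) dilute the rate in the same way.

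**The case against.** The case against has several good parts.

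- **Baseline is reported separately.** The sentence in Section 10.5.5 names three counts and does not make the any-time count the main one. This stands: pre-existing antibodies will be visible.
- **Period 2 is largely unaffected.** This stands. The only gap there is a subject positive at baseline who remains positive. The phrase about subjects who have developed antibodies hints at exclusion but is not defined.
- **By-visit output may already be planned.** SAP Section 10.1 summarizes data by time, as appropriate, at protocol time points, so day 22 and day 29 could appear separately. This stands in part. Section 10.5.5 does not promise it, and counts at each visit do not show which subjects changed from negative to positive. The listings would, but only by hand.
- **Nothing is decided on this endpoint.** No hypothesis is tested (SAP Section 5), no stopping rule uses antibodies, and antibody data go to dose review only if available (SAP Appendix F). This stands, and it limits the weight of the point.
- **The design itself confounds route.** Even a day 29 positive follows three weeks of cIV. This stands, and any new definition must say so.

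A reader might infer that the plan would report pre-existing or cIV-induced antibodies as SC immunogenicity throughout the study. The documents do not support that. No count is labelled as SC-induced, baseline positives are shown apart, and Period 2 post-baseline samples in cycle 1 all follow SC.

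**Conclusion.** The point holds for Period 1. With baseline fixed at day 1, the post-baseline count mixes samples taken before SC, after SC and after resumed cIV, and the default analysis set includes subjects never given SC. None of the three planned summaries answers the stated objective. For Period 2 cycle 1 the point reduces to the handling of persistent baseline positives.

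The practical size is probably small. One pre-SC positive in a cohort of 6 changes 0/5 into 1/6, but that positive is an assumption, and the protocol reports none under cIV in NHL. The conclusion rests on reading Section 10.5.5 with the SAP's general baseline and analysis-set rules, since that section sets no others. It does not depend on the assumed positivity rates.

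**What to change.** Add an SC-emergent antibody incidence to SAP Section 10.5.5.

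- **Event:** negative at the last pre-SC sample (day 22 predose in Period 1, day 1 predose in Period 2) and positive at a later sample taken before any further cIV. In Period 1 that is the cIV-restart sample. In Period 2 it is the samples in weeks 3 to 6 and the follow-up or pre-cycle-2 sample.
- **Denominator:** SC-treated subjects with a negative pre-SC sample and at least one such later sample.
- **Shown separately:** pre-SC positives, and positives first seen after cIV resumes (Period 1 follow-up, or any cIV cycle 2), marked as not attributable to SC alone. Counting any later positive as SC-emergent would bring the mixing of routes back.
- **Stated limit:** Period 1 attribution is weakened by the prior cIV run-in and rests on a single sample after SC and before cIV.

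Keep the three existing counts as supportive. Also state how the follow-up sample after an SC cycle 2 in Period 2 is handled, since it too precedes any cIV.

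The cost is one definition and one table. All the samples are already scheduled.

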10.5.6 Exposure to Investigational Product

Descriptive statistics will be produced to describe the exposure to investigational product by dosing schedule for cIV and SC separately. The number of cycles, number of doses of investigational product and the total dose in μg will be summarized.

Details for each blinatumomab administration will be listed for every subject. In addition, a listing of the unique manufacturing lot numbers, and a listing of the subjects administered each manufacturing lot number will be provided.

10.5.7 Exposure to Concomitant Medication

All medication will be coded using the WHO drug dictionary. A subject listing of all prior and concomitant medications will be presented.

10.6 Efficacy Analyses

Statistical analyses of efficacy endpoints will be considered secondary. Efficacy data will be conducted on the Full Analysis Set.

10.6.1 Analyses of Secondary Efficacy Endpoint(s)

The efficacy endpoint of the study is ORR (CR+PR) after blinatumomab treatment based on [Chesons' 2007](#) criteria ([Appendix B](#)). The analysis is based on the response evaluation recorded in the CRF for subjects in the full analysis set. Subjects will be considered as non-responders if there is no response assessment available. The rate will be estimated along with its 95% Clopper-Pearson exact confidence interval by dose group and overall. Subject listings with related collected parameters will also be provided.

Summary of other best responses status by each response category will be also provided. The number and percentage of subjects with a disease response of complete response (CR), partial response (PR), stable disease (SD) or progressive disease (PD) will be presented for the dose escalation and/or expansion parts of the study.

Subject listings with related collected parameters will also be provided.

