### Exploratory Endpoints:

PD parameters of B- and T-lymphocytes and cytokines following administration of SC blinatumomab

ORR (CR + PR) as determined by best overall response using Lugano criteria ([Appendix B](#))

Approved

**Study Design:** This is a global multi-center, Phase 1b open-label study investigating the safety and PK of blinatumomab administered subcutaneously for the treatment of relapsed/refractory indolent NHL. The SC administration of blinatumomab will be tested for the first time in humans.

Period 1 of the study will focus on the determination of PK, bioavailability, and safety profile of blinatumomab SC administration. The PK and bioavailability data from Period 1 of the study will be used in conjunction with safety data (DLT) to determine the SC MTD. The MTD or the maximum tested dose, if MTD is not reached, will be further tested in Period 2 in an expanded cohort. Efficacy of blinatumomab administered subcutaneously will also be investigated in each period of the study.

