## 2.4 Rationale

[figure not shown]
The effect of blinatumomab in the treatment of NHL was tested in a dose escalation study (Study MT103-104 [Goebeler et al, 2016]). A dose dependent clinical response was observed and objective clinical responses were seen starting at 15  $\mu\text{g}/\text{m}^2/\text{d}$  (~28  $\mu\text{g}/\text{day}$ ) and peaked at 60  $\mu\text{g}/\text{m}^2/\text{d}$  (~112  $\mu\text{g}/\text{day}$ ). Due to transient cytokine release after initiation of treatment, a step-dosing regimen was implemented to minimize cytokine related adverse events. An effective step-dose regimen of 9  $\mu\text{g}/\text{d}$  (week 1)-28  $\mu\text{g}/\text{d}$  (week 2)-112  $\mu\text{g}/\text{d}$  (remaining weeks) following cIV infusion for 8 weeks was established for the treatment of diffuse large B-cell lymphoma in study MT103-208 (Viardot et al, 2016). In this study, the blinatumomab concentration levels following the cIV regimen will be used as a reference to guide dose selection of SC administration. The target SC dose for the treatment of NHL is a dose that can achieve a similar exposure (area under the curve) as that of 112  $\mu\text{g}/\text{d}$  dose under cIV. To facilitate the SC dose selection, PK simulation was performed with the PK parameters (clearance and volume of distribution) generated from human studies under cIV and an assumed bioavailability of 0.25 in humans which was an approximate average of bioavailability in mouse (0.35), rat (0.16), monkey (0.21) and pig (0.30) under SC administration.

The simulated PK profiles of cIV (9/28/112  $\mu\text{g}/\text{d}$ ) and SC every day (112/450) and twice a day ([BID] 56/225  $\mu\text{g}/\text{dose}$ ) are provided in Figure 3. Based on currently available information on bioavailability and exposure, 450 (or 225  $\mu\text{g}/\text{BID}$ ) is the estimated SC equivalent dose to the cIV 112  $\mu\text{g}/\text{d}$  dose.

The assumption will be examined in Period 1 of this study following the PK assessment in the cIV run-in phase and then SC administration.

The calculated bioavailability for SC administration, the PK profiles of SC as well as safety and tolerability data will be used to assess the doses recommended for the Period 2 of the study.

**Figure 3. Simulated Blinatumomab Concentration-time Profiles Under Continuous IV Infusion and Under Once (1a) or Twice (1b) Daily Subcutaneous Administrations**

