## 3. EXPERIMENTAL PLAN

### 3.1 Study Design

The overall study design is described by study schemas in Figure 1 and Figure 2 at the end of the protocol synopsis section.

This is a global multi-center, Phase 1b open-label study investigating the safety and PK of blinatumomab administered subcutaneously for the treatment of relapsed/refractory indolent NHL. The SC administration of blinatumomab will be tested for the first time in humans.

Approximately **30** subjects' evaluable for dose limiting toxicities (DLT) will be enrolled in Period 1 (6 evaluable subjects in each dose-cohort). The focus of this period is to determine the PK, bioavailability, and safety profile of blinatumomab SC administration. The PK and bioavailability data from Period 1 of the study will be used in conjunction with safety data (DLT) to determine the SC MTD. The MTD or the maximum tested dose, if MTD is not reached, will be further tested in Period 2 in an expanded cohort of up to 15 additional **evaluable** subjects. Efficacy of blinatumomab administered subcutaneously will also be investigated in each period of the study.

### 3.1.1 Cycle 1/Period 1

In Period 1, **3 or more** separate dose cohorts of up to 6 DLT evaluable subjects each will be enrolled. Subjects will undergo an initial cIV blinatumomab run-in period (weeks 1 to 3) followed by **a 12-hour treatment free period, and then receive** SC administration (week 4). After **a treatment free period of 2 to not more than 3 days**, subjects receive cIV treatment to complete 6 weeks of therapy (weeks 5 to 6) **Figure 1**.

For all cohorts, the initial cIV dose of blinatumomab will be 9 µg/day for the first 7 days (to mitigate for potential cytokine release syndrome [CRS] and neurologic events associated with introduction to blinatumomab) which then will be escalated (dose-step) to 28 µg/day starting on day 8 through day 14 (week 2), and to 112 µg/day starting on day 15 until day 21 (week 3).

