**If ≥ 2 subjects within any Cycle1/Period 1 cohort experience a DLT, the remaining subjects enrolled in that cohort that have not reached the SC week 4 of Cycle 1/Period 1 will not receive any SC but can continue on cIV dosing to complete 6 weeks of IV treatment.**

Approved

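### Neither the overall ORR nor any Period 1 ORR in SAP 10.6.1 measures SC efficacy, and the Period 2 rate that could do so is not secured

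*SAP*

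**What the plan says.** **Objective.** SAP 2.2 (and Protocol 1.2) gives as a secondary objective: "To evaluate efficacy response following treatment with SC blinatumomab administration". The Protocol synopsis, repeated in Protocol 3.1 and SAP 3.1, adds: "Efficacy of blinatumomab administered subcutaneously will also be investigated in each period of the study".

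**Period 1 treatment.** SAP 3.1: "Subjects will undergo an initial cIV blinatumomab run-in period (weeks 1 to 3) followed by a 12-hour treatment free period". SC dosing occupies week 4, and cIV at 112 µg/day resumes for weeks 5 and 6. Optional Cycle 2 in Period 1 is cIV.

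**Period 2 treatment.** Cycle 1 is SC only, in up to 15 evaluable subjects. Optional Cycle 2 is SC if scans show benefit and cIV if they do not (Protocol 6.2.1.1.3).

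**Timing of response.** Disease is imaged at screening and not again until Cycle 1 is over (Protocol Table 3 and 7.3.10; SAP section 6, Best Overall Response).

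**Analysis.** SAP 10.6 places efficacy on the full analysis set. SAP 10.6.1: "The rate will be estimated along with its 95% Clopper-Pearson exact confidence interval by dose group and overall". SAP 7.1 groups escalation subjects by the first blinatumomab dose they received, and expansion subjects by the dose chosen for expansion. Protocol 10.1.2 and 10.4.1 summarise by planned or assigned cohort.

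**Subjects without SC.** If a Period 1 cohort has two or more subjects with a DLT, those not yet at week 4 (Protocol 6.2.1.4.2, after Table 2) "will not receive any SC but can continue on cIV dosing to complete 6 weeks of IV treatment". They remain in the full analysis set.

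**The concern.** A Period 1 response cannot be credited to the SC week. It follows three weeks of cIV before that week and two weeks after it, with no scan in between to separate them. The cIV part is active treatment. Protocol 2.4 says of the earlier cIV dose-escalation study in NHL: "A dose dependent clinical response was observed and objective clinical responses were seen starting at 15" µg/m²/day (about 28 µg/day), with a peak at about 112 µg/day. The same section calls the 9/28/112 step regimen effective, although that statement concerns diffuse large B-cell lymphoma treated for eight weeks.

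Two misreadings are possible. The overall rate could be taken as the SC response rate when most of its subjects had mainly cIV. A trend across Period 1 cohorts could be taken as an SC dose-response when the planned cIV is the same in every cohort.

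The SAP separates routes elsewhere. Period 1 adverse events are tabulated for SC and cIV separately (SAP 10.5.1), and PK is grouped by dose, period and route (SAP 10.7). Efficacy has no such split.

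**Working it through.** **1. The plan's own number.** SAP 3.2 and Protocol 3.3 give about 54 enrolled, to yield about 30 evaluable in Period 1 and up to 15 in Period 2, with about 20% premature discontinuation. 45 × 1.20 = 54, so the figure reproduces. Split the same way, it is 30 × 1.20 = 36 in Period 1 and 15 × 1.20 = 18 in Period 2. The documents state no ORR target or precision, so there is no efficacy figure to reproduce.

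**2. Share of Period 1 dosing days that are SC (cohorts 1-3).** cIV days = 21 + 14 = 35. SC days = 5. Share = 5/40 = 12.5%. Any bridging days added so that SC starts on a Monday lower this share. Under q7d, SC is a single injection.

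**3. Share of Period 1 exposure that is SC.**
- cIV dose = 9×7 + 28×7 + 112×7 + 112×14 = 2611 µg.
- SC dose = 112×9 = 1008 µg, 225×9 = 2025 µg and 450×5 = 2250 µg in cohorts 1, 2 and 3.
- Share = F×SC / (F×SC + 2611), with the bioavailability F assumed in Protocol 2.4 and its animal range.

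| F | Cohort 1 | Cohort 2 | Cohort 3 |
|---|---|---|---|
| 0.16 | 6% | 11% | 12% |
| 0.25 | 9% | 16% | 18% |
| 0.35 | 12% | 21% | 23% |

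**4. Weight of Period 1 in the overall rate.** 30/45 = 36/54 = 67%. Write p1 for the Period 1 rate and p2 for the SC-only rate. The overall rate is (2/3)p1 + (1/3)p2, so its error as an SC estimate is (2/3)(p1 − p2). If p1 is below p2, it understates SC.

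**5. Illustration on full-analysis-set denominators.** The response counts are assumptions, because the documents give none. Period 1 is held at 22/36 (61%). Intervals are 95% Clopper-Pearson.

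| Period 2 alone | Overall |
|---|---|
| 11/18 = 61% (36-83%) | 33/54 = 61% (47-74%) |
| 7/18 = 39% (17-64%) | 29/54 = 54% (40-67%) |
| 4/18 = 22% (6-48%) | 26/54 = 48% (34-62%) |
| 0/18 = 0% (0-19%) | 22/54 = 41% (28-55%) |

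In the last row, no response at all on SC alone would still give an overall rate of 41%.

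**6. Subjects with no SC dose.** Protocol 3.3 places the expected Period 1 losses in the cIV run-in. That is about 36 − 30 = 6 of 36 who may count without any SC, plus anyone in a halted cohort.

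**7. Is the Period 2 rate secured?** Three texts leave it open.
- By SAP 7.1, every escalation subject falls under the same initial dose, 9 µg/day cIV. Protocol 10.4.1 would instead use assigned cohort. The two do not agree.
- Period 2 uses the dose selected in Period 1. If groups are labelled by SC dose, a Period 1 cohort and the expansion can share a label, and nothing says they are kept apart. The CR/PR/SD/PD counts are promised for the escalation and/or expansion parts, which does not commit to both.
- The definition of best overall response refers to the safety follow-up visit after Cycle 1 and to a scan before any Cycle 2. For a subject who has Cycle 2, however, that visit moves to after Cycle 2 (Protocol Table 5, footnote c), and Protocol 7.3.10 schedules a scan there. A Period 2 subject without benefit on SC who then responds to cIV is not clearly excluded.

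**The case against.** The best reply is that the quoted sentence plans rates by dose group as well as overall. SAP 7.1 puts expansion subjects under the expansion dose, and Protocol 10.1.2 keeps planned cohorts separate. On an ordinary reading, a Period 2 ORR with an exact interval is already planned. The aim of Period 2 is stated to include preliminary efficacy on SC alone, while the focus of Period 1 is PK, bioavailability and safety. This largely stands. A reader might infer that the plan yields no SC efficacy estimate at all, and the documents do not support that.

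A second reply is that nothing presents the overall rate as the headline or as an SC rate. Protocol 10.4.2 and SAP 10.6.1 describe ORR after blinatumomab treatment, without naming a route. No hypothesis is tested (SAP section 5), efficacy is secondary, and no ORR threshold or decision rule exists. This also stands, and it limits the severity. It does not remove the mismatch with the objective and with the sentence promising SC efficacy in each period.

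A reader might also infer that run-in dropouts are definitely counted under an SC dose group. SAP 7.1 would place them under the initial cIV dose, while Protocol 10.4.1 would place them under their assigned cohort. What is certain is only that they enter the full analysis set and hence the overall rate.

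**Conclusion.** The point holds with a limited reach. The overall ORR and every Period 1 ORR are mixed-route rates and do not answer the SC efficacy objective. In cohorts 1-3, SC is 12.5% of planned dosing days and about 9-18% of exposure at F = 0.25 (6-23% over the animal range). Period 1 carries two-thirds of the pooled rate, so the overall figure misses the SC-only rate by two-thirds of the difference between periods. The direction is unknown in advance.

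A Period 2 rate is probably produced, but grouping, separation of periods and handling of Cycle 2 all need to be fixed in writing before it can be relied on as SC-only.

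The day and dose shares assume the planned schedule is completed. The weights assume planned enrolment, and the ORR illustrations rest on assumed response counts. Severity is should-fix: ORR is a descriptive secondary endpoint with no decision rule, and the primary safety endpoint is unaffected.

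**What to change.** In SAP sections 6, 7.1 and 10.6.1 and Protocol 10.4.2:

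1. Name Period 2 Cycle 1 ORR, with response assessed before any Cycle 2, as the estimate for the SC efficacy objective.
2. Report Period 1 ORR separately, by assigned SC cohort, as response after sequential cIV/SC/cIV treatment. List subjects who never received SC. Replace the initial-dose grouping in SAP 7.1 for this purpose.
3. Drop the cross-period overall ORR, or label it as mixed-route and not an SC estimate.
4. Report responses after Cycle 2 separately, by the route given in Cycle 2.
5. Align the sentence on SC efficacy in each period (Protocol synopsis and 3.1, SAP 3.1) with the above.

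The Lugano ORR in SAP 10.6.2 uses the same methods and would follow.

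**Cost.** Wording in several places in both documents, with no new data or visits. The SC estimate then rests on about 15 to 18 subjects. Its exact interval is about ±25 points at mid-range rates (for example 6/15 = 40%, 16-68%; 7/18 = 39%, 17-64%), against about ±14 for the pooled 54. That width reflects how little SC-only efficacy information the trial collects.
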